15.5.2.3 Pain and PRO Assessment

The hypothesis in this study is that FIS will induce a systemic anti-inflammatory and senolytic effect, thereby reducing pain and improving self-reported function and quality of life compared to the placebo group. Early subjective assessment (every 3 days for 6 weeks following the first dose of study medication and once weekly for the following 6 weeks) will be limited to a short augmented numerical rating scale questionnaire. Linear mixed-effect random-intercepts modeling will be used to characterize the trend in self-reported pain over 3 months, and to test whether treatment group is a significant predictor of pain reduction.

The IKDC, WOMAC, Tegner activity scale and Lysholm PRO measures will be administered at 2 weeks after the last dose of study medication and 6, 12, and 18 months following initiation of medication. For each time point, ANCOVA will be used with the subject's baseline PROM value used as a covariate. Among the 4 postoperative time-points for assessing these validated PROMs, the Holm-Bonferroni method will be used to control the family-wise type-1 error rate to 0.05 within each PROM scale tested. No multiplicity adjustments will be made across different PROMs, which are commonly highly intercorrelated.

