6.0 Summary of Proposed Placebo Controlled Trial

Our objective is to determine (through the performance of an adequate and well-controlled clinical trial) if the administration of Fisetin (FIS) safely reduces inflammation and pain, reduces senescent cell burden, mitigates cartilage degeneration, and improves joint function in patients with moderate to severe OA of the knee.

Patients suffering from OA of one or both knees will be recruited from the clinical practice of the Principal Investigator at TSC. Patients diagnosed with Kellgren-Lawrence grade II-IV OA of the knee via radiographic analysis, who meet all enrollment criteria will be offered the opportunity to participate in this study.

At the first visit, each potential subject will be fully informed regarding all aspects of the proposed study and will be required to review and sign a full, IRB approved, Informed Consent Form (ICF) attached as **Appendix A in Section 22.1**. Subjects who sign Informed Consent will be screened by a member of the Study Team. The patients' medical record will be reviewed to determine if medical history indicates that the eligibility criteria are met. If so, subjects will be screened for OA and senescent cells by T-Cell assay, C12FDG Flow assay, and by senescence biomarker assay. Further blood analyses will be performed.

Subjects who meet eligibility criteria will be assigned, 1:1 via block randomization, to one of the two blinded study groups. FIS and the inactive placebo are collectively referred to as Study Medication.

n=36: Active Treatment: FIS: 100 mg capsules (~20 mg/ kg/ day);

n=36: Placebo Control: Appearance matched capsules (dose to match the number of capsules as if subjects were receiving active treatment).

At visit two, Quantitative MRI, kinematic movement and strength testing, range of motion (ROM) and functional performance testing. Subjects will complete numerous patient reported outcomes tools, including an augmented patient reported outcomes (PROs), including numerical rating scale (NRS) for pain (as described in **Section 11.5**) of this protocol International Knee Documentation Committee (IKDC), Lysholm, Tegner, Western Ontario McMaster Universities Osteoarthritis Index (WOMAC) and short form-12 health survey (SF-12), which will provide a baseline assessment of joint pain and function.

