8.2.2 Secondary Endpoints

Statistically significant as compared to placebo:

1. Improvement in serum measures of inflammation and cartilage degenerating SASP markers;
2. Improvement in lower-extremity kinematic testing with video-motion analysis; isokinetic dynamometry testing, functional performance testing, ROM;
3. Improvement in IKDC, Lysholm, TEGNER, WOMAC and SF-12 surveys;
4. Improvement in the quality of articular cartilage in the knee joint as measured by T2 and T1rho relaxometry;
5. Days from day one of Study Medication intake to conversion to alternative therapy.

Additionally, we will review and discuss any possible correlation among secondary endpoint results.

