11.5 Patient Reported Outcomes (PROs): (Visits 1, 2, 4, 5, 6)

All PROs may be completed either on paper documents or by online questionnaire administration conducted via formsite (Vroman Systems, Inc.). Patients may complete questionnaires on a variety of electronic devices (personal computer, mobile phone, tablet).

PRO data to be collected include:

Augmented Numerical Rating Scale (NRS) (visit 2): At baseline then once every 3 days during FIRST 6 weeks of study medication treatment then once a week for an ADDITIONAL 6 weeks.

IKDC, Lysholm, TEGNER, WOMAC and SF-12 (visit 2, visits 4, 5, and 6 and remote assessments at 3- and 18-months post completion of medication).

The Numerical Rating Scale is a simple 0-10 self-reported severity of pain scale, (zero being no pain and 10 being the worst pain imaginable). This tool has been validated to provide excellent test-retest reliability in assessing knee pain associated with OA³¹. The Steadman Philippon Research Institute has added several stand-alone questions that are administered with the questionnaire. Only the validated portion, the simple NRS will be used to screen patients. In follow-up, each question will be analyzed individually. There is no composite score. A sample can be found in **Appendix C, Section 22.3** of this document.

The Lysholm knee scale is a condition-specific outcome measure that was originally designed to assess ligament injuries of the knee. It has been tested to provide excellent construct validity and overall acceptable psychometric performance for outcomes assessment of various chondral disorders of the knee. It is recommended that this tool be administered with additional psychometric measurements^{32,33}.

The TEGNER Activity Scale is a numerical scale ranging from 0 to 10. Each value indicates the ability to perform specific activities. An activity level of 10 corresponds to participation in the most physically demanding activities while a zero is assigned if a person is on sick leave or receiving a disability pension because of knee problems. It is simple to use, and it has been demonstrated to provide acceptable psychometric performances as outcome measures for patients with a meniscal injury of the knee. Like the Lysholm, it is recommended that it be used in conjunction with other psychometric tools such as the SF 12³².

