15.4 General Data Handling, Analysis, and Reporting Strategy

Intent-to-treat analysis will be performed.

Baseline covariates will be summarized and reported in a table, stratified by group. This is a randomized trial, thus the expected population group differences with respect to baseline covariates are zero by definition. For this reason, no statistical comparisons will be performed to test for differences in baseline covariates between groups.

Whenever applicable, assessment of endpoints that are measured at serial time points will be analyzed using methods that account for this repeated measure structure. Listwise deletion in response to missing data points and categorization/dichotomization of continuous measurements will be avoided to every extent possible.

Summary statistics will be reported as group medians with quartiles or extrema. Meanwhile estimates calculated for statistical inference will be reported with $(1-\alpha)\%$ confidence intervals. Model fit and satisfactorily meeting model assumptions will be assessed for all multivariable regression and linear mixed-effects models using residual analysis.

The Statistical Computing Language R will be used to produce all analyses and plots.

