15.5.2 Secondary Endpoints

15.5.2.1 Imaging Assessment of OA

Quantitative MRI will be performed at baseline and at 6 months and 12 months after initiation of medication. T2 and T1rho relaxometry will be performed. Linear mixed-effects modeling with random intercepts will be used to appropriately match the repeated measures design. A group-by-time interaction will be modeled to investigate both early improvement in tissue quality and maintenance of such an effect to 12 months as well.

Secondarily, multivariable modeling techniques such as support vector machines (SVM) and/or principal components analysis (PCA) will be pursued to characterize the SASP response profile that distinguishes the FIS and placebo groups.

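### The 12-week pain-diary analysis names no tested coefficient or time coding, and a linear group-by-time test in its random-intercept-only model would understate the standard error

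*Combined protocol and SAP*

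**What the plan says.** Section 15.5.2.3 states two uses of one model for the diary. The first is that "Linear mixed-effect random-intercepts modeling will be used to characterize the trend in self-reported pain over 3 months"; the second is "to test whether treatment group is a significant predictor of pain reduction". It names no random slope, residual correlation structure or robust standard error. It also does not say which coefficient carries the test or how time enters.

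Section 11.5 gives the schedule: "At baseline then once every 3 days during FIRST 6 weeks of study medication treatment then once a week for an ADDITIONAL 6 weeks".

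The MRI analysis in section 15.5.2.1 is more explicit: "A group-by-time interaction will be modeled to investigate both early improvement in tissue quality". The diary paragraph has no matching statement.

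Section 15.4 adds two general provisions. Serial endpoints "will be analyzed using methods that account for this repeated measure structure", and "Model fit and satisfactorily meeting model assumptions will be assessed for all multivariable regression and linear mixed-effects models using residual analysis". It does not say what follows if a check fails.

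On the weight of the diary, section 6.0 puts pain in the study objective (whether the drug "safely reduces inflammation and pain"). The patient-reported item among the numbered secondary endpoints in section 8.2.2 reads "Improvement in IKDC, Lysholm, TEGNER, WOMAC and SF-12 surveys", which leaves out the numerical rating scale. Section 15.6 sizes the trial on a T1rho effect, not on pain.

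**The concern.** A random intercept lets subjects differ in level. It treats everything else in a subject's diary as independent noise around a common slope per arm. Two features that a pain diary can easily have break this: subjects improve or worsen at different rates, and records three days apart resemble each other more than records weeks apart. Section 12.1 itself expects symptoms that fluctuate in severity and duration.

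Neither feature matters much for a comparison of average level, because the random intercept absorbs the between-subject variation. Both matter for a comparison of linear slopes. There the model counts many records per subject as nearly independent information on the slope, when the real unit of information is the subject.

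At stake is a false-positive early pain trend. Section 11.5 says each question of the augmented scale is analysed separately, and Appendix C has three 0-to-10 pain ratings, so the same issue could arise more than once. The primary safety analysis and the questionnaires analysed by ANCOVA are not touched.

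**Working it through.** **The plan's own figures.** The documents give no variance, power or error figure for the diary, so there is none to reproduce. The one computable design figure is 30 per group in section 15.6: 2 × (1.960 + 0.842)² / 0.73² = 29.5, so 30. It reproduces by the normal approximation but does not bear on the diary.

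**Inputs from the documents**
- Record times (sections 11.5 and 15.5.2.3): day 0; days 3 to 42 in steps of 3 (14 records); days 49 to 84 in steps of 7 (6 records). That is m = 1 + 14 + 6 = 21.
- With time in weeks, the sum of squares about the mean time is Sxx = 250.
- 36 per arm (sections 6.0 and 15.6).

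**Assumptions**
- Two-sided 5% level. Section 15.6 states it for the sample size; no level is given for the diary.
- Intercept SD 1.5 and residual SD σ = 1.2 rating-scale points, with σ = 0.8 and 2.0 as alternatives.
- SD of true slopes τ from 0 to 0.10 points per week, or 3-day residual correlation ρ from 0 to 0.7.
- No drug effect and complete diaries, unless stated.

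**Closed form for the linear slope test.** With balanced data, the group-by-linear-time estimate in a random-intercept model is the difference in mean within-subject slopes.
- True variance: (2/n)(τ² + σ²/Sxx).
- Variance the model reports: (2/n)(σ² + τ²Sxx/(m − 1))/Sxx.
- Ratio: R = (σ² + τ²Sxx) / (σ² + τ²Sxx/(m − 1)).
- Actual error: 2Φ(−1.96/√R).

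R does not contain n, so enrolling up to the cap of 100 would not help. For serial correlation, replace the numerator by x′Vx/Sxx and the denominator by the average within-subject variance, where x is centred time and V the residual covariance.

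Worked case, σ = 1.2 and τ = 0.05: τ²Sxx = 0.0025 × 250 = 0.625. R = (1.44 + 0.625)/(1.44 + 0.625/20) = 2.065/1.471 = 1.404. √R = 1.185, and the error is 2Φ(−1.654) = 9.8%.

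| Setting | Error of slope test |
|---|---|
| No departure | 5% |
| σ = 1.2; τ = 0.03, 0.05, 0.08, 0.10 | 7%, 10%, 17%, 22% |
| σ = 1.2; ρ = 0.3, 0.5, 0.7 | 10%, 16%, 28% |
| σ = 0.8; τ = 0.05, 0.10 | 15%, 33% |
| σ = 2.0; τ = 0.05, 0.10 | 7%, 12% |

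Simulation with 20,000 runs per setting agreed to within about half a percentage point.

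**Other readings of the test, same settings**
- Group main effect: 4.7% to 5.3% throughout.
- Joint group-by-categorical-time test: 5% to 6% for the slope departures at σ = 1.2 (8% at σ = 0.8 with τ = 0.10); 6%, 8% and 11% at ρ = 0.3, 0.5 and 0.7.

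**Candidate remedies for the slope test**
- Small-sample-corrected cluster-robust errors by subject: 4.9% to 5.4% with complete diaries; about 5% to 6% with 10% missed entries and 5% to 20% drop-out (assumed rates).
- Random intercept and slope with continuous-time AR(1) residuals: 3% to 6%, with and without drop-out.
- Unweighted per-subject slopes: 5% with complete diaries. With 10% missed entries and 10% or 20% drop-out, their standard error is about 1.6 or 2.7 times the cluster-robust one, and the error falls to about 2% to 4%. Early leavers with few records have very noisy slopes that count as much as complete ones.

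**Width.** The ratio of valid to model-based standard error is 1.18 and 1.58 at τ = 0.05 and 0.10, and 1.17, 1.40 and 1.80 at ρ = 0.3, 0.5 and 0.7. Over all settings it runs from 1.06 to 2.02.

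**The case against.** The best defence is textual. In section 15.5.2.3 the trend belongs to a descriptive clause, and the clause that announces a test names treatment group as the predictor. The MRI paragraph shows that the authors write out a group-by-time interaction when they intend one. On that reading the diary test is a group main effect, its error is near 5%, and the model needs no change. This stands as a possible reading, but it does not settle the matter. The tested outcome is pain reduction, which describes change, while a main effect on pain level estimates an average difference in level.

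Second, section 15.4 already asks for methods suited to repeated measures and for residual checks on every mixed model. Such a check could reveal the misfit. What remains is that no action is stated, so any remedy would be chosen after the data are seen.

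Third, the percentages rest on assumed variances. That is correct. The range is an illustration, not a bound: no slope variation gives 5%, and more slope variation than assumed here gives more than 33%.

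A reader might infer that the trial's early pain test will have a false-positive rate of 7% to 33%. The documents do not support that, because they fix neither the coefficient nor any pain variance. Nor does this point show a fault in the MRI model.

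**Conclusion.** The firm finding is that section 15.5.2.3 commits to random intercepts for about 21 records per subject without naming the tested coefficient or the time coding. The conditional finding is that a linear group-by-time test in that model is anti-conservative whenever slopes vary between subjects or nearby records are correlated. Under the assumed variances its error is 1.3 to 6.7 times the nominal 5% (6.7/5 and 33.3/5). A main-effect test is sound, and a joint categorical-time test is affected much less.

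The consequence is limited. The diary supports the pain part of the objective but is neither a numbered secondary endpoint nor the sample-size basis. This is an improvement the sponsor could make, with medium confidence because the intended test is not stated.

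**What to change.** In section 15.5.2.3:
- State whether the group main effect or a group-by-time term is tested, and whether time is linear or categorical.
- Keep the mixed model, which uses incomplete diaries as section 15.7 intends.
- Base inference on any group-by-time term on cluster-robust standard errors by subject with a small-sample correction. Alternatively, fit a random intercept and slope with continuous-time AR(1) residuals and name the cluster-robust errors as the fallback.
- Do not substitute unweighted per-subject slopes, which lose precision and become conservative when diaries are incomplete.

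If the group main effect is the test, stating so is enough. No change to the MRI model is proposed.

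The cost is wording only, with no new data, visits or subjects. Intervals for a slope difference become about 1.2 to 1.8 times wider under the main assumed departures. The narrower intervals given up would not have held their stated level under those departures.

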15.7 Missing Data

Whenever possible, statistical methods such as linear mixed-effects modeling which naturally handle missing data will be utilized. Missing data will be investigated carefully by the biostatistician, the study manager and the clinical staff to assess its probable cause, and whether missing not at random (MNAR, missingness dependent on outcome), missing at random (MAR, missingness not dependent

on outcome but can be fully accounted for by other non-missing covariates) or missing completely at random (MCAR, missingness independent of both observed variables and unobserved parameters of interest) is most likely.

If any missing data patterns are determined to be MNAR, this observance will be reported narratively in the final report(s) and publication(s), and no imputation methods will be pursued. Little's test will be used to assess whether missing values are missing completely at random (MCAR). For methods that require complete data or listwise deletion (e.g. PCA), and where missing data is determined to be reasonably missing at random (MAR or MCAR), multiple imputation using predictive mean matching will be employed.

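### Separate per-visit ANCOVAs for the PROs depart from the plan's own preference for repeated-measures models, and can understate the late effect if dropout follows earlier scores

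*Combined protocol and SAP*

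**What the plan says.** Section 15.5.2.3 has the four scales "administered at 2 weeks after the last dose of study medication and 6, 12, and 18 months following initiation of medication". The analysis is: "For each time point, ANCOVA will be used with the subject's baseline PROM value used as a covariate". Across the four times, the "Holm-Bonferroni method will be used to control the family-wise type-1 error rate to 0.05 within each PROM scale tested".

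Three general statements bear on this choice:

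- Section 15.4, for cases where it is applicable: "assessment of endpoints that are measured at serial time points will be analyzed using methods that account for this repeated measure structure".
- Section 15.4 again: "Listwise deletion in response to missing data points and categorization/dichotomization of continuous measurements will be avoided to every extent possible".
- Section 15.7: "Whenever possible, statistical methods such as linear mixed-effects modeling which naturally handle missing data will be utilized".

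Section 15.7 also has a fallback. It begins "For methods that require complete data or listwise deletion (e.g. PCA), and where missing data is determined to be reasonably missing at random" and then prescribes multiple imputation by predictive mean matching. If missingness is judged not at random (MNAR), nothing is imputed and the pattern is only described in the report.

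Mixed models are already planned for quantitative MRI (15.5.2.1) and for the three-month series of pain ratings (15.5.2.3, in the paragraph before the ANCOVA text).

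**The concern.** Four unconnected fits make no use of the correlation between a subject's visits. A subject with scores at two weeks, 6 and 12 months but none at 18 months contributes nothing to an unimputed 18-month ANCOVA, although those scores say a good deal about the missing one.

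Loss in this trial could be related to outcome. Under 15.5.2.4, subjects who convert to a regenerative or surgical treatment leave the study, and section 15.6 allows for 20% drop-out or incomplete follow-up. If those who leave had poorer earlier scores, the subjects left at the late visits are selected, and baseline adjustment alone does not remove the selection. If the selection is stronger on placebo, the remaining placebo subjects look too good and a real benefit is partly hidden.

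**Working it through.** **1. The plan's own figure.** Section 15.6 gives 30 per group for a standardised difference of 0.73, two-sided alpha 0.05 and 80% power. By the normal approximation, n = 2(1.960 + 0.842)² / 0.73² = 29.5, so 30; it reproduces. (By the exact t calculation, power is 79.4% at 30 and 80.7% at 31.) This figure concerns T1rho MRI. The documents give no effect size, power or dropout rate for any PRO, so it neither supports nor weakens the present point.

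**2. Subjects in an unimputed late ANCOVA.** With 36 per group (30 + 6 in 15.6) and 20% loss: 0.80 × 36 = 28.8 per arm, about 57 or 58 of 72. With 50 per group (the cap of 100): 0.80 × 100 = 80.

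**3. Effect on the 18-month estimate.** This was simulated. From the documents: four follow-up visits, baseline covariate, 36 per arm, 20% loss. Assumed, because the documents are silent: equal correlation of 0.5 to 0.7 between visits, a constant true effect of 0.50 or 0.73 SD, loss without return, and, where loss depends on a score, log-odds of 1.5 per SD towards losing poorer scorers. The complete-case ANCOVA is compared with a joint likelihood model using all observed visits with unstructured covariance.

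| Loss depends on | True effect (SD) | ANCOVA | Joint model |
|---|---|---|---|
| Nothing (completely at random) | 0.73 | 0.733–0.734 | 0.732–0.735 |
| Previous observed score, both arms | 0.50 | 0.46–0.48 | 0.49–0.51 |
| Previous observed score, placebo only | 0.50 | 0.42–0.43 | 0.49–0.51 |
| Previous observed score, both arms | 0.73 | 0.685 | 0.726–0.733 |
| Previous observed score, placebo only | 0.73 | 0.643–0.664 | 0.727–0.734 |
| As above, 30% loss, correlation 0.7 | 0.73 | 0.629 | 0.728 |
| As above, 20% loss, no true effect | 0 | −0.076 | −0.006 |
| Current, unseen score | 0.50 | 0.39–0.46 | 0.41–0.47 |

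Shortfall of ANCOVA at a true effect of 0.50: from 0.50 − 0.48 = 0.02 to 0.50 − 0.42 = 0.08 SD. At 0.73 and 20% loss, taking the gap to the joint model in the same runs: from 0.726 − 0.685 = 0.041 to 0.727 − 0.643 = 0.084 SD.

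**4. Precision.** Under completely random loss the empirical standard errors are 0.237 (ANCOVA) and 0.234 (joint) at correlation 0.5, and 0.189 and 0.183 at 0.7. The variance ratios are (0.237/0.234)² = 1.03 and (0.189/0.183)² = 1.07. With score-dependent loss the ratio is 1.00 to 1.02. The cost in variance is therefore between nil and about 6 to 7%.

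**5. Scale of the bias.** Against a standard error of about 0.19 to 0.23, a shortfall of 0.02 to 0.08 is between 0.02/0.23 = 0.09 and 0.08/0.19 = 0.42 standard errors.

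**6. Unseen worsening.** In the last row of the table the joint model improves on ANCOVA by only 0.01 to 0.02 SD, and by at most about 0.04 in other runs of this kind. It still falls short by 0.50 − 0.47 = 0.03 to 0.50 − 0.41 = 0.09 SD.

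**The case against.** The strongest reply is the fallback in 15.7. A per-visit ANCOVA is a complete-data method and PCA is only named as an example, so on its terms the imputation rule covers these analyses. That stands to this extent: a reader might infer that the plan discards every subject who misses a visit, and the documents do not fix that. But the fallback does not settle the matter:

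- Section 15.5.2.3 does not refer to it.
- It lapses if missingness is judged MNAR. Section 15.7 explains MNAR as missingness that depends on outcome, so loss driven by earlier observed scores, which a likelihood model can handle as missing at random, could be classed as MNAR and left unimputed.
- Nothing says that other visits' scores enter the imputation model.
- In simulations of loss following earlier scores (true effect 0.50), predictive mean matching recovered little: 0.43–0.48, against 0.44–0.49 for ANCOVA and 0.50–0.51 for the joint model.

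Other replies also stand. The statements in 15.4 and 15.7 are qualified, so this is a departure from a stated preference; a reader who sees a breach of an absolute ban on listwise deletion goes further than the text. The documents give no conversion rate and no dropout mechanism. The 20% was set for the MRI sample size, while PROs can be completed remotely (11.5, 13.4) and at 18 months need no clinic visit (10.6.2). It is therefore not established that late visits will lose the worst-off subjects. Repeated testing is not at issue either, since Holm covers the four times within each scale. Finally, these are secondary endpoints in a small Phase I/II trial.

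**Conclusion.** The point holds as an unexplained departure from the plan's own preference, with a conditional and modest consequence. A repeated-measures model was applicable, since the plan uses one for two other serial endpoints. If loss depends on earlier observed scores and imputation does not correct for it, the 18-month effect is understated by roughly 0.02 to 0.08 SD, under the assumed effect of 0.50 SD, 20% loss and correlations of 0.5 to 0.7. If loss is completely at random or depends only on arm and baseline score, the ANCOVAs are unbiased and only a little precision is lost.

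A reader might also infer that a mixed model would remove the bias from conversions. The documents do not support that: the decision to convert may follow worsening since the last recorded score, and in that case the mixed model corrects only slightly. The change is worth making because it is cheap, but it needs a sensitivity analysis beside it.

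**What to change.** In 15.5.2.3, replace the four ANCOVAs with one mixed model for repeated measures per scale. The terms are baseline score, visit, baseline-by-visit, group and group-by-visit, with unstructured covariance and Kenward-Roger degrees of freedom. Read the group contrast at each of the four visits and keep Holm across those four.

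Add a sensitivity analysis for data missing not at random, for example imputation with a shift applied to unobserved scores and varied by arm. Section 15.7 now rules out imputation in that case, so it needs an exception. It should also say that loss explained by earlier observed PRO scores counts as missing at random.

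The cost is SAP wording and slightly more modelling work. The data, visits and contrasts stay the same. The change should be made before the group labels are added to the data (15.8).
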